PROJECT SCHEDULE

Copeptin- Relevance as a Perioperative Marker in Pediatric Cardiac Surgery

[name]

n1150639

Department of Cardiac Surgery

Medical University of Vienna

[name],

[name]

Supervisor:

Dr. med. univ. [name]

[contact]

Dr. med. univ. [name]

TABLE OF CONTENT**1.**

1. Summary	3
2. Background	4
3. Aims of this study	6
4. Study population	6
5. Methods	7
6. Statistical analysis	8
7. Ethical aspects	9
8. Data handling and record keeping	10
9. Time schedule	10
10. Additional contributers	11
References	11

2.

1. Summary

Objective:

Vasopressin is a hormone secreted by the posterior pituitary gland. Its main functions are the constriction of blood vessels and reabsorption of water and thereby regulating water balance and hemodynamics of the body. Copeptin is a cleavage product in the synthesis of vasopressin and is being released in equimolar amounts. Its stability makes it easier to determine than vasopressin.

The use of a heart-lung machine in cardiac procedures has important effects on the water balance of the body and affects vasopressin secretion.

This prospective clinical trial aims to figure out if copeptin would be suitable for perioperative risk evaluation in neonates and children with congenital heart disease after surgery with the use of a heart-lung machine.

Hypotheses:

The primary outcome endpoint of this study is the change in copeptin concentration perioperatively in patients with congenital heart disease, with the use of heart-lung machine.

Secondary outcome endpoints are correlations between copeptin concentration and complexity of the procedure (based on the aristotle basic score), clinical status and the perfusion times of the heart-lung machine.

Material and Methods:

The study population consists of 81 subjects, newborns, infants and children up to six years of age with congenital heart disease, undergoing surgery with the use of a heart lung machine.

To determine the main outcome variable, three blood samples will be taken from each patient perioperatively in order to evaluate changes in copeptin concentration.

Relevance and Implications:

This will be the first study focusing on correlations of copeptin concentrations with different variables in pediatric cardiac surgery. Findings may allow to use copeptin perioperatively to evaluate the clinical and hemodynamic situation of patients after congenital heart surgery.

2. Background

Vasopressin - Synthesis and Secretion:

Vasopressin is a polypeptid built of 9 amino acids. It is synthesized in the magnocellular neurons, the paraventricular nucleus and supraoptic nucleus of the anterior hypothalamus. These neurons have axonal projections which connect to the posterior pituitary gland where the hormone is carried through.

After posttranslational processing the product, prepro-AVP-NPII, is being cleaved by endopeptidases into AVP, neurophysin II (95 amino acids) and copeptin (39 amino acids) in equal amounts. By opening voltage-gated calcium channels, neurosecretory granules start fusing with the nerve terminal membrane and release AVP, NPII and copeptin in equimolar amounts into the circulation.

Neurophysin and copeptin have no known role in peripheral tissues. Since both polypeptides are being released in equal amounts, copeptin can be used as a reliable surrogate marker for vasopressin secretion.

Studies also showed that copeptin is elevated in critically ill patients, after myocardial infarction, septic shock and chronic heart failure.

Cellular Action

Vasopressin binds to G-protein-coupled receptors called vasopressin receptors that are classified into V1, V2 and V3 subtypes. The V1 receptor is found in vascular smooth muscle, liver, platelets and central nervous system and is Gq-mediated and therefore results in an increase of intracellular calcium which leads to vasoconstriction. The V2 receptor is expressed on the basolateral membrane of the collecting ducts of the kidney and stimulates movement of aquaporin-2 to the apical membrane, which allow reabsorption of water. The V3

receptor is found in the anterior pituitary gland and acts synergistically with CRF causing secretion of ACTH.

Copeptin

The measurement of AVP is technically challenging because of its instability and the large amount attached to platelets. Therefore copeptin is used as a surrogate marker. It can be measured in serum and plasma samples by sandwich immunoassay. Its ex vivo stability for at least 7 days in serum and citrate-, EDTA-, and heparin plasma at 4°C was demonstrated. Studies also showed that there is no association in copeptin levels with age.

Heart-Lung Machine

The heart-lung machine takes up the perfusion work of the heart and additionally oxygenates the carried blood. It is a vital tool in cardiac surgery and enables complex procedures to be performed.

It is important to pay close attention to the effects of the heart-lung machine in the postoperative period including: volume shift from intravasal to interstitial, peripheral vasoconstriction, myocardial depression and altered hemodynamics without adaption to recent flow conditions. Therefore it also affects synthesis and secretion of vasopressin.

3. Aims of this study

This prospective clinical trial aims to assess changes in copeptin levels perioperatively in patients with congenital heart disease undergoing corrective or palliative surgery with the use of a heart-lung machine by analysis of three blood samples of each patient.

4. Study population

The study population consists of 81 patients (neonates, infants, children) with congenital heart disease and the need of surgery with a heart-lung machine.

Parental consent after pre-operation discussion and informing of the study is required.

Exclusion criteria are following: need of preoperative mechanical circulatory support, preoperative mechanical ventilation, Diabetes insipidus, preoperative cardio pulmonary resuscitation, no consent of the parents and preoperative shock or sepsis.

5. Methods

After induction of anesthesia every patient undergoing cardiac surgery will get monitored by vascular access. The anesthesiologist will place an arterial catheter for invasive blood pressure and a central venous catheter for applying medication and measurement of central venous pressure. We are planning to use these catheters for taking the blood samples which means that we will not place an additional syringe for the study.

For measurement of copeptin 900 μ l of blood is taken at three different time points. The first sample will be taken before the surgery in the operation room. The second sample will be taken after the surgery in the operation room and the third sample, one day after the surgery in the intensive care unit. The exact times will be recorded in report sheets.

After the surgery the cardiopulmonary bypass times and the exact procedures will be recorded. The performed procedures are needed in regard to calculating the Aristotle score which determines the complexity of the procedure.

The extubation time and the length of stay in the intensive care unit as well as any important events (any complications) in the postoperative period are going to be recorded.

The samples will be stored at the Meduni Wien Biobank until all samples are collected. After collection of these data for 81 patients the samples will be analyzed by the laboratory and the collected data will be prepared for statistical analysis.

Sample size

Sample size calculation was performed based on a paired t-Test. Due to a prior study we knew that the major change of copeptin concentration would be between the first and second measurement. Assumptions of the needed variables were estimated based on this study.

As a result a sample size of 73 patients will have 80% power to detect a difference in means of -0,25 (e.g. a first condition mean, m_1 , of 0,086 and a second condition mean, m_2 , of 0,336), assuming a standard deviation of differences of 0,75, using a paired t-test with a 0,05 two-sided significance level. Based on clinical experience the dropout rate will be determined at 10%. That implies a total sample size of 81 patients.

6. Statistical analysis

Descriptive Statistics

Statistical analysis will be performed using SPSS. Variables for the description of the population are the distribution of age, gender and weight. For describing numerical data of age and weight will be used, dependent on the distribution, means and standard deviations or median and minimum-maximum values.

Surgery related variables for further descriptive statistics are cardiopulmonary bypass time, aortic cross clamp time and complexity level of aristotle score. Cardiopulmonary bypass and aortic cross clamp time will be described by either mean or median depending on the distribution.

Postoperative data variables for descriptive analysis are length of ICU stay (in days), intubation time (in hours). Length of ICU stay and intubation time will be shown by either mean or median depending on the distribution.

Descriptive statistics of copeptin values consist of mean values and standard deviations of the logarithmized collected data. Three Scattergrams of the logarithmized data will be displayed of the first and second measurement, first and third measurement and second and third measurement.

Relevant descriptive data will be graphically shown in an appropriate manner.

Table of descriptive variables

Variables	Units	Variable type
Age	in years	metric
Gender	girl/boy	nominal
Weight	in kg	metric
CPB Time	in minutes	metric
AoXC Time	in minutes	metric
Complexity level	1-4	ordinal
LOS- ICU	in days	metric
Intubation Time	in hours	metric
Copeptin	in ng/ml	metric

Analytical statistics of copeptin values

Since three samples at different times will be taken of one patient, we are going to compare paired means. To compare the copeptin levels of the first and the second measurements, will be used paired t-test with a 0,05 two-sided significance level. Analyses will be performed using SPSS.

The null hypothesis implies that the means of the first and the second measurements are not significantly different. The alternative hypothesis implies that the difference of both means is significant. As copeptin is not expected to be normally distributed, logarithmic e-transformations will be performed.

This test will be repeated for the second and the third measurements and for the first and the third measurements.

Correlations

Secondary outcome endpoints are correlations between copeptin concentration and complexity of the procedure (based on the aristotle basic score), clinical status (based on length of ICU stay and intubation time) and the perfusion times of the heart-lung machine.

Pearson's correlations coefficient will be used for calculating the correlation of copeptin concentrations with intubation time (in hours), length of ICU stay (in days), the aristotle basic score of each procedure and the times of the heart-lung machine. Data of each correlation will be shown in a scattergram.

7. Ethical aspects

We tried scheduling this study without any disadvantages or discomfort for the subjects. Vascular access for the blood samples will be placed by the anesthesiologists for every patient undergoing cardiac surgery.

Also the amount of blood needed for copeptin measurement will be calculated as low as possible.

Prior to inclusion in the study parents will be asked for written informed consent. Parents or participants can decide to withdraw from the study at any time and can also be removed from the trial by the investigator if exclusion criteria are met. No side effects are expected from taking this amount of blood samples.

The study will be performed in accordance with the Declaration of Helsinki (1964), including all current revisions, and the guidelines for Good Scientific Practice required by the Medical University of Vienna.

First application for approval of this study and all other procedures involved by the Ethics Committee of the Medical University of Vienna will be made in January 2017.

8. Data handling and record keeping

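### Sampling times are recorded but no analysis uses them, so variation in the interval to the third sample goes unadjusted in the comparisons and correlations that use it.

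*Combined protocol and SAP*

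**What the plan says.** Section 5 (Methods) places samples 1 and 2 in the operating room, before and after surgery. It describes the last draw as "the third sample, one day after the surgery in the intensive care unit", with no hour, reference event or window. It then adds "The exact times will be recorded in report sheets".

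Section 6 does not return to those times. The table of descriptive variables has no sampling or elapsed time. Under Analytical statistics of copeptin values, the 1-2 comparison is a paired t-test on natural-log copeptin, and "This test will be repeated for the second and the third measurements and for the first and the third measurements". Under Correlations, the sentence beginning "Pearson's correlations coefficient will be used for calculating the correlation of copeptin concentrations with intubation time (in hours" goes on to ICU stay, the Aristotle basic score and the heart-lung machine times. All the coefficients are unadjusted. The plan does not say which of the three samples enters them.

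**The concern.** The plan itself expects copeptin to move during the perioperative period. If the level is still moving on day 1, part of each third-sample value reflects how many hours had passed when it was drawn. Two consequences follow, and they rest on different conditions.

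- **Noise.** Any spread in the interval widens the 2-3 and 1-3 differences. This needs only that copeptin is still changing and that intervals vary.
- **Bias in correlations.** This needs more: the interval must be related to the other variable, and third-sample copeptin must be the value correlated. For example, if day-1 blood were drawn at a fixed clock time, a longer operation would leave fewer hours to sample 3. With copeptin falling, those patients would read higher, and a positive correlation with bypass time or complexity would appear from timing alone.

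At stake are two of the three paired comparisons and the secondary correlations. The information needed to deal with the problem is already collected but has no planned use.

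**Working it through.** **1. The plan's own figure.** Section 5, Sample size, states that "a sample size of 73 patients will have 80% power" "to detect a difference in means of -0,25", "assuming a standard deviation of differences of 0,75", "using a paired t-test with a 0,05 two-sided significance level". By the noncentral t distribution with noncentrality (0.25/0.75) × √n, power is 0.802 at n = 73 and 0.797 at n = 72, so 73 reproduces. With 10% dropout, 73/0.9 = 81.1, against the stated 81. The calculation concerns samples 1 and 2 only, so third-sample timing does not enter it.

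**2. Assumptions for the size.** The documents give neither a rate of return nor a spread of intervals. The following are assumed for illustration:
- The excess over the preoperative level halves every h = 6, 12, 24 or 48 h, and sample 3 is drawn about 24 h after surgery.
- The interval SD is 4 h, and its correlation with bypass time is 0.6 in absolute size.
- The SD of log copeptin is 0.75, borrowed from the plan's SD of paired differences.
- The planned means 0.086 and 0.336 carry no stated scale, so three readings are tried for R, the ratio of postoperative to preoperative level. Natural log gives e^0.25 = 1.284, log10 gives 10^0.25 = 1.778, and raw concentrations give 0.336/0.086 = 3.907.

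**3. Formulas.**
- Log elevation at t hours: E(t) = ln[1 + (R − 1) × 2^(−t/h)].
- Hourly slope at 24 h: s = (ln 2/h) × u/(1 + u), with u = (R − 1) × 2^(−24/h).
- Effect of drawing at 18 h instead of 24 h: E(18) − E(24).
- Spurious correlation: r = 0.6 × 4s / √(0.75² + (4s)²).
- False-positive rate: Fisher z with n = 73, two-sided 0.05.
- Effective n, taking a wider interval SD of 6 h: 73 × 0.75² / (0.75² + (6s)²).

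**4. Largest case in full (raw reading, h = 12).** u = 2.907 × 0.25 = 0.727 and s = 0.0578 × 0.727/1.727 = 0.0243. The 6 h effect is ln 2.028 − ln 1.727 = 0.161. With 4s = 0.097, r = 0.6 × 0.097/0.756 = 0.077, and the rejection rate is 9.9%. With 6s = 0.146, effective n = 73 × 0.5625/0.5838 = 70.3.

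**5. Ranges over h = 6 to 48 h.**

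| Reading of the planned means | 6 h effect on ln copeptin | Spurious r | False-positive rate | Effective n |
|---|---|---|---|---|
| Natural log | 0.015 to 0.027 | 0.006 to 0.012 | 5.0 to 5.1% | 72.9 to 73.0 |
| Log10 | 0.032 to 0.065 | 0.016 to 0.030 | 5.2 to 5.7% | 72.6 to 72.9 |
| Raw concentration | 0.059 to 0.161 | 0.031 to 0.077 | 5.8 to 9.9% | 70.3 to 72.6 |

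**6. Cost of adjusting.** If the interval correlates 0.6 with bypass time, the variance inflation is 1/(1 − 0.6²) = 1.56, about 1.6.

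**The case against.** The strongest reply is that the effect may be negligible. If the planned rise of 0.25 is in log units, little is left to decline by day 1, and the table shows almost nothing on either log reading. That stands for those readings. It does not settle the matter, because the Sample size text does not name the scale and the raw reading gives up to about 10% false positives.

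The second reply is that the bias path is conditional. No section says day-1 blood is drawn at a fixed clock time. The wording can equally mean about 24 h after surgery, which would break the link with operation length. If sample 2 is the value correlated, third-sample timing is irrelevant. All of this stands, so the bias is a possibility that the plan does not exclude and cannot be called a demonstrated defect.

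The third reply concerns the remedy. Bypass time is listed in minutes, a duration, and nothing shows that the clock time at which bypass ends is kept. Hours from end of bypass may therefore be unavailable. The interval from sample 2 to sample 3 can still be computed from the recorded draw times.

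A reader might infer a much larger effect by letting the whole concentration halve every 12 h. That gives r of about 0.18, 32% false positives and, at an interval SD of 6 h, an effective n of about 60. The documents do not support this. It means decay toward zero instead of a return toward baseline, and a fall of 24 × ln 2/12 = 1.39 log units by 24 h. That exceeds the planned 1-2 rise on every reading (0.25, 0.58 or 1.36), although the plan expects the largest change between samples 1 and 2.

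**Conclusion.** The gap is real: elapsed time is collected, varies by an unstated amount, and appears in no table, test or correlation. On the stated assumptions its cost runs from nil to modest, with spurious r about 0.01 to 0.08, a false-positive rate of about 5 to 10% at n = 73, and effective n about 70 to 73. These figures are illustrative. The half-life, the interval spread, the 0.6 correlation and the use of 0.75 as a cross-sectional SD are all assumed, and the upper end needs the raw reading of the planned means.

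A reader might also infer that the paired tests or the sample size are compromised. They are not. A paired t-test remains a valid test of mean change at the times actually sampled, so only precision and interpretation suffer. The primary 1-2 comparison uses two operating-room draws and does not involve sample 3. This is a cheap improvement to the 2-3 and 1-3 comparisons and the secondary correlations.

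**What to change.** In Section 6:
- Compute the hours from sample 2 to sample 3 from the report sheets (or from end of bypass, if that clock time is recorded), and add their distribution to the descriptive variables.
- For the 2-3 and 1-3 comparisons, regress the paired log difference on the mean-centred hours. The intercept then equals the mean paired difference, so the planned estimate is kept while timing spread is removed from the residual.
- For each correlation that uses third-sample copeptin, report the partial correlation adjusted for these hours beside the planned Pearson coefficient, and state which sample enters.

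The cost is SAP wording and one degree of freedom per analysis, with no extra blood or patients. The downside is some loss of precision in the adjusted correlations if the interval is collinear with bypass time (variance inflation about 1.6 at correlation 0.6), which is why both coefficients should be shown. Specifying this before analysis avoids a post hoc adjustment.

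### Do the two repeated paired t-tests need a stated role, their own sizing or a planned confidence interval?

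*Combined protocol and SAP*

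**What the plan says.** Section 1 (Hypotheses) words the endpoint broadly: "The primary outcome endpoint of this study is the change in copeptin concentration perioperatively in patients with congenital heart disease". It names no pair of time points. Under Material and Methods the same section links the endpoint to every sample: "To determine the main outcome variable, three blood samples will be taken from each patient perioperatively".

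The narrowing comes later. Section 5 (Sample size) relies on a prior study from which the authors expected that "the major change of copeptin concentration would be between the first and second measurement". The calculation follows from that: "As a result a sample size of 73 patients will have 80% power to detect a difference in means of -0,25", with a standard deviation of differences of 0.75 and a two-sided 0.05 level.

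Section 6 (Analytical statistics of copeptin values) specifies the paired t-test for first against second, on log-transformed values, and writes hypotheses for that pair alone: "The null hypothesis implies that the means of the first and the second measurements are not significantly different". It then adds the other two pairs: "This test will be repeated for the second and the third measurements and for the first and the third measurements".

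The Correlations part of section 6 opens with "Secondary outcome endpoints are correlations between copeptin concentration and complexity of the procedure", and its list contains correlations only. On reporting, the descriptive part says: "Descriptive statistics of copeptin values consist of mean values and standard deviations of the logarithmized collected data". It also plans scattergrams for each of the three pairs. No confidence interval is mentioned.

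**The concern.** Read on its own, section 6 runs the same 0.05 test three times, while section 1 defines the primary endpoint loosely enough for any pair to satisfy it. The two repeats appear in neither the primary wording nor the list of secondary endpoints, so a reader cannot look up their standing.

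Two misuses seem possible.

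- If first against second were not significant, a significant repeat could be presented as meeting the primary endpoint.
- A non-significant first against third could be read as a return to the starting level, or a non-significant second against third as no further change, although neither comparison was sized. With p-values alone, the reader would not see how wide the uncertainty is.

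At stake would be the false-positive rate of the main claim and the reading of the intensive care sample taken one day after surgery.

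**Working it through.** **Inputs.** From section 5: n = 73, difference 0.25 (0.336 − 0.086), standard deviation of differences 0.75, two-sided 0.05. The plan does not state the scale of these figures. They are taken here as log units; power depends only on the ratio 0.25/0.75. Assumed, because the documents give no figures: a standard deviation of differences of 0.75 for the other two pairs, equal variances with correlation 0.5 between all pairs of time points, and a range of positions for the third mean.

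**Reproducing the plan's figure.** Noncentrality = difference × √n / SD = 0.25 × √73 / 0.75 = 2.848; critical t on 72 df = 1.993. Power from the noncentral t is 80.2%; with 72 patients it is 79.7%. The stated 73 is right.

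**Power of a repeat at n = 73, SD 0.75.** Same formula:

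| True difference | Noncentrality | Power |
|---|---|---|
| 0.25 | 2.848 | 80.2% |
| 0.20 | 2.278 | 61.3% |
| 0.15 | 1.709 | 39.2% |
| 0.125 | 1.424 | 29.0% |
| 0.10 | 1.139 | 20.3% |

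At a difference of 0.125, an SD of 0.6 gives 41.9% and an SD of 0.9 gives 21.6%.

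**Both repeats non-significant.** Simulated with first against second fixed at 0.25, SD 0.75, correlation 0.5, moving only the third mean:

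| Third mean | Both repeats non-significant |
|---|---|
| 0.125 below the first | 1% |
| Equal to the first | 18% |
| One quarter of the way to the second | 36% |
| Halfway | 45% |
| Three quarters of the way | 36% |
| Equal to the second | 18% |
| 0.125 above the second | 1% |

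The 45% is the peak of the positions tried. Nothing in the plan places the third mean halfway.

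**False positives.**

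- First against second alone: 5%.
- Any of the three, if all three means are equal and any significant pair were allowed to count: the bound is 3 × 0.05 = 15%; three independent tests would give 1 − 0.95³ = 14.3%; simulation with correlation 0.5 gives about 12%.
- If first and second differ, as section 5 expects, the third mean cannot equal both. At most one repeat then has a true null, so a false positive among the repeats has probability at most about 5%.

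**Interval.** Half-width = 1.993 × 0.75 / √73 = 0.175. For complete pairs the mean difference is the difference of the two log means, and its standard error is that difference divided by the t statistic. If t is reported, the 95% interval therefore follows from the planned output. Example: a mean difference of 0.125 with standard error 0.75/√73 = 0.0878 gives t = 1.42 and an interval of 0.125 ± 0.175, that is −0.050 to 0.300.

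**The case for a change.** The best case for a change is that the omissions are real and cheap to fill. No sentence calls first against second primary, section 1 points to all three samples, and the repeats have no listed status. The third sample invites the question of whether copeptin has come back down. If the truth lies in between, each repeat has only 29% power, and in up to 45% of trials both would be non-significant, which could be misread as both returned and unchanged. The interval half-width of 0.175 exceeds the 0.125 difference at issue; an interval would show this and a p-value does not. A few sentences would settle it.

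The facts and the arithmetic stand. The inference to a defect does not.

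- The primary contrast follows from the sizing and from the only hypotheses written down.
- The 45% belongs to the least favourable third mean among those tried, within a range of 1% to 45%.
- Follow-up contrasts without their own sample size are ordinary, and these have the same 80.2% power for the difference the trial was designed around, given the assumed SD.
- The hypotheses concern difference only. No equivalence claim is planned, so the feared misreading is one the plan does not make.
- Labelling the repeats secondary would introduce an inconsistency, because sections 1 and 6 reserve that term for the correlations.

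**Conclusion.** This is a gap in labelling that a competent analyst fills sensibly: first against second is the primary test, the other two pairs are supporting description, and each mean log difference can be shown with its interval. Followed as written, the plan gives a primary test with 5% error and 80.2% power at 73 patients. The 12% any-of-three error needs all means equal, against the expectation in section 5, and a rule that any pair may count, which the plan does not contain. The lower power of the repeats for small differences is real (29% at 0.125) and is a matter for careful wording of the results.

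The power and interval figures for the repeats rest on an assumed SD of 0.75 for those pairs; the joint and any-of-three simulation figures also rest on an assumed correlation of 0.5. The identification of the primary contrast and its 5% error do not depend on either assumption. No change to the plan follows.

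### The Pearson correlations are specified on copeptin concentrations with no mention of the ln transformation that the plan uses for the t-tests and descriptives; read literally, the secondary correlations would probably be weaker and more sensitive to a few high values

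*Combined protocol and SAP*

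**What the plan says.** All of this is in the combined protocol and SAP, section 6 (Statistical analysis).

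- **Analytical statistics of copeptin values**, in the text on the paired t-tests: "As copeptin is not expected to be normally distributed, logarithmic e-transformations will be performed". The next sentence extends the t-test to the other two pairs of measurements.
- **Descriptive Statistics**: "Descriptive statistics of copeptin values consist of mean values and standard deviations of the logarithmized collected data". The three scattergrams of one copeptin measurement against another are also to be drawn on logged data.
- **Correlations**: Pearson's "correlations coefficient will be used for calculating the correlation of copeptin concentrations with intubation time". The sentence goes on to ICU stay in days, the Aristotle basic score and the heart-lung machine times. Each correlation is to be shown in a scattergram. The paragraph mentions no log scale, rank-based alternative or check of distribution.

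The table of descriptive variables lists copeptin in ng/ml. Descriptive Statistics leaves open whether ICU stay, intubation time, bypass time and cross-clamp time are summarised by mean or median, so the plan does not commit itself on their shape.

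**The concern.** The plan gives a reason for logging copeptin, its expected non-normality, and that reason applies equally to a Pearson coefficient. Where the authors want the log scale in the descriptives, they say so. In the Correlations paragraph they do not, so the natural reading is copeptin in its measured units.

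Pearson's coefficient on a right-skewed marker gives much of its weight to the few largest values. If the relation is closer to linear in ln copeptin, the raw-scale coefficient also understates it. The correlations are the only declared secondary endpoints, and the only planned analyses that link copeptin to procedural complexity, perfusion time and clinical course. They could therefore come out weaker than they need to be, and on a different scale from the primary comparison. An unstated scale also lets the analyst choose between the two versions after seeing the data.

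**Working it through.** **1. The plan's own figure.** The documents give no power figure for the correlations. The only stated calculation is for the primary test (section 5, Sample size): "a sample size of 73 patients will have 80% power to detect a difference in means of -0,25", "assuming a standard deviation of differences of 0,75", "using a paired t-test with a 0,05 two-sided significance level". With the noncentral t distribution and standardised difference 0.25/0.75 = 0.333, power is 79.7% at n = 72 and 80.2% at n = 73, so 73 is reproduced. Allowing for 10% dropout, 73/0.9 = 81.1, against the stated 81. The scale of copeptin in the correlations does not enter this calculation. I take n = 73 as the evaluable number below.

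**2. Range for the SD of ln copeptin at one time point (assumption).** The documents do not give it. The only SD is 0.75, for paired differences, and its scale is not stated. If it is on the ln scale, the SD at one time point is s = 0.75/√(2(1 − c)), where c is the within-patient correlation:

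- c = 0 gives s = 0.53
- c = 0.5 gives s = 0.75
- c of about 0.72 gives s = 1.0
- c of about 0.84 gives s = 1.33

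**3. Large-sample attenuation.** Assume that ln copeptin is normal with SD s, that the correlate is normal, and that their correlation is ρ. The covariance of raw copeptin with the standardised correlate is ρ·s·exp(s²/2) times the geometric mean. The SD of raw copeptin is exp(s²/2)·√(exp(s²) − 1) times the geometric mean. Hence

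raw-scale r = ρ · s/√(exp(s²) − 1).

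For s = 0.75: exp(0.5625) = 1.755, √0.755 = 0.869, and 0.75/0.869 = 0.863.

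**4. Size at n = 73, ρ = 0.30, two-sided 0.05.** For ln copeptin, Fisher's approximation gives atanh(0.30)·√70 = 0.3095 × 8.367 = 2.59. Then 2.59 − 1.96 = 0.63, which is a power of about 74%. Simulation (20,000 replicates) agrees, and gives for raw copeptin:

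| Assumed s | Factor | Large-sample r | Mean r at n = 73 | Power, raw | Power, ln |
|---|---|---|---|---|---|
| 0.53 | 0.93 | 0.28 | 0.28 | 68% | 74% |
| 0.75 | 0.86 | 0.26 | 0.26 | 63% | 74% |
| 1.0 | 0.76 | 0.23 | 0.25 | 56% | 74% |
| 1.33 | 0.60 | 0.18 | 0.22 | 47% | 74% |

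Repeat runs move the power figures by about one percentage point. At n = 73 the attenuation is milder than the large-sample factor when s is large.

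**5. Dependence on high values.** Under the same assumptions, the three most extreme of 73 patients carry a median 48%, 58% and 70% of the raw copeptin sum of squares for s = 0.75, 1.0 and 1.33. On the ln scale they carry 23%.

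**6. Skewed correlate.** If the correlate is lognormal with ln-scale SD s₂ and is left raw, then

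raw–raw r = (exp(ρ·s·s₂) − 1)/√((exp(s²) − 1)(exp(s₂²) − 1)).

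With s = 0.75 and s₂ = 1.0:

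- ρ = 0.7 gives 0.61 raw–raw, against 0.53 for ln copeptin with the raw correlate.
- ρ = 0.3 gives 0.22 against 0.23.

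So the raw coefficient is not always the smaller one. Simulated at n = 73 and ρ = 0.30 with s₂ = 1.0, power is 52% to 38% with raw copeptin over the range of s, about 57% with copeptin alone logged, and about 74% with both logged. In the skewed-correlate simulations the sampling SD of r is 0.13 to 0.16 raw and 0.11 with ln copeptin.

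**7. No association.** With ρ = 0, the type I error stayed near 5% in every scenario simulated, raw or logged.

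**The case against.** The strongest reply is that the plan never says raw or untransformed. The transformation sentence gives a property of copeptin as its reason and does not limit itself to the t-test, so it could cover the correlations. The word concentration settles nothing: the Summary uses it for the primary endpoint, which is tested after ln transformation. This stands to the extent that the raw scale is an inference. It does not remove the need to state the scale, since the sentence sits with the t-tests and the Correlations paragraph is silent.

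A reader might infer that every secondary correlation is pulled toward zero. The documents do not support that. They do not give the shape of the correlates or the scale on which any relation is linear, and step 6 shows cases where the raw coefficient equals or exceeds the half-logged one. Nor do they show that a few high values would drive the results. They contain no copeptin data, so this is a risk, and the planned scattergrams would make influential points visible.

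Two further objections also stand. The size rests on an SD that the plan does not give, with a modest loss at the mild end (74% to 68%). Logging copeptin alone would not fully repair correlations with skewed durations. Finally, these are secondary analyses with no stated power target and no inflation of type I error. That limits the importance of the point but does not remove it.

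**Conclusion.** The point holds in a limited form. The plan logs copeptin for the t-tests and descriptives because it expects non-normality, and does not carry this into the Correlations paragraph. Read literally, the secondary correlations would probably be weaker and more sensitive to a few high values than they need be. Over the assumed range of s, the loss of power at a true correlation of 0.30 is about 6 to 27 percentage points (74% to between 68% and 47%). This requires lognormal copeptin, a relation linear in ln copeptin, a normal correlate and 73 evaluable patients. With other correlate shapes, or a relation linear on another scale, the loss may be smaller or absent. The primary comparison and the sample size of 73 (81 with dropout) are untouched. The change is worth making before the analysis, but it does not threaten the main result.

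**What to change.** In section 6, Correlations:

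- Name *ln-transformed copeptin* as the variable for all correlates, in place of copeptin concentrations, and draw the correlation scattergrams on that scale.
- State that skewed correlates, such as ICU stay and intubation time, will be log-transformed, or that Spearman's coefficient will be used for them. Choose one in advance.

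The same sentence could also name which of the three measurements, or which change, is correlated; the paragraph does not say.

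The cost is a few words in the plan, with no new data and no change in sample size. The downside is that the correlations are then read on the log scale, or as rank correlations where Spearman's coefficient is used, and no longer in ng/ml.
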